3.4. Endpoints and covariates

The primary outcome is death from any cause at hospital discharge. Secondary outcomes include death from any cause within 6 and 24 hours, and neurological outcomes assessed using the Glasgow-Pittsburgh Cerebral Performance Category values at hospital discharge. Covariates considered in the analysis include demographics and significant clinical variables such as age and sex.

3.5. Handling of missing data

Cases with missing data were excluded from the study as part of the pre-analysis data cleaning process. The study aimed to maintain the integrity and reliability of the analysis by ensuring that only complete and accurate data sets were utilized in the evaluation.

3.6. Statistical procedures

All data were presented by the mean with standard deviation for continuous variables and frequency with percentage for categorical variables. The independent two-sample t-test, chi-squared or Fisher's exact test were used to compare differences in continuous or categorical

variables between the two groups. The Cox proportional hazards regression and logistic regression model were used to assess primary and secondary outcomes. The survival probability was estimated using Kaplan–Meier method, and the survival curves were compared between CtD time of <30 min and CtD time of ≥ 30 min groups by the log-rank test. Propensity-score matching and multivariable analyses were also utilized to adjust for confounding variables and assess the impact of CtD time on clinical outcomes. Landmark analysis also was conducted at 24 hours after hospital arrival. Data manipulation and statistical analyses were conducted using SAS version 9.3 (SAS Institute) and R software (version 4.1.1; R Foundation for Statistical Computing, Vienna, Austria). Statistical significance was set at $P < 0.05$. An independent statistician will conduct all statistical analyses to ensure objectivity and accuracy in the interpretation of the data.

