2.5. Sample size calculation

Between 2016 and 2021, 182,508 patients have been included in the Korea OHCA registry. Of these about 28% have been non-cardiac origin, about 0.5% have been under 18 years of age, about 25% has been did not receive any CPR, and about 4% has been missing data. Thus we assume that about 42% i.e. 76,505 patients will fulfil the inclusion criteria without exclusion criteria

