2.6. Hypothesis

- 1) The study hypothesizes that a delayed time interval between primary emergency call and hospital arrival (Call-to-door time[CtD]) is significantly associated with decreased survival rates and unfavorable neurological outcomes in OHCA patients.
- 2) The COVID-19 pandemic has exacerbated the delays in CtD time, further hindering timely treatment and negatively impacting the survival rates and outcomes of OHCA patients.
- 3) The study aims to meticulously explore and quantify the impact of various delayed factors on the prognosis of patients experiencing OHCA, to provide a more comprehensive understanding of their influence.

3. Statistical Analysis Plan

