3.1. Data source

The data for this study was sourced from the Korea OHCA Registry, a collaborative database established by the Korea Centers for Disease Control and Prevention and the central fire services under the Korean government leadership.

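### Section 3.6 makes no allowance for clustering by EMS service, region or receiving hospital; if call-to-door time and outcome both cluster, standard errors are too small

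*Combined protocol and SAP*

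**What the plan says.** Section 3.6 holds the whole analysis specification. For the outcomes it says that "The Cox proportional hazards regression and logistic regression model were used to assess primary and secondary outcomes". It adds two-group t, chi-squared or Fisher tests, Kaplan–Meier curves with a log-rank test at a 30-minute CtD cut, propensity-score matching, multivariable analyses and a landmark at 24 hours, all judged at the 0.05 level. It names no variance estimator and no term or stratum for EMS service, region or hospital.

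Section 3.4 makes death from any cause at hospital discharge the primary outcome. Its covariate list is open-ended, with age and sex as the only examples.

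Section 2.6 defines the exposure as the interval from the emergency call to hospital arrival. Section 3.1 describes the data source as "a collaborative database established by the Korea Centers for Disease Control and Prevention and the central fire services". Section 2.5 gives the expected size: "Thus we assume that about 42% i.e. 76,505 patients will fulfil the inclusion criteria without exclusion criteria". No section gives the number of services, regions or hospitals, an ICC, an event rate, or the share of patients at or above 30 minutes.

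**The concern.** CtD time is not a purely personal characteristic. It depends on how an EMS service is organised and on the distance to a receiving hospital, so patients served by the same units will tend to have similar values. Survival to discharge depends in part on care in that hospital. When exposure and outcome both vary between the same units, patients within a unit carry overlapping information about the association, and a standard error that ignores this is too small.

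The large sample makes this matter more. Sampling error is small, so modest effects reach significance, and large clusters let small ICCs build up into a material design effect. Differences between areas or hospitals could then be reported as a precise CtD effect.

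**Working it through.** **Expected sample size.** Section 2.5 starts from 182,508 registry patients and lists exclusions of 28%, 0.5%, 25% and 4%.
- Summing the exclusions: 182,508 × (1 − 0.28 − 0.005 − 0.25 − 0.04) = 77,566, which is 1.4% above the stated 76,505.
- Using the rounded share: 182,508 × 0.42 = 76,653, which is 0.2% above.

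So 76,505 is a usable expected N. The plan has no power calculation to reproduce.

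**Formula.** For a patient-level exposure that varies within and between K clusters of equal size m = 76,505/K:
- Design effect DE = 1 + (m − 1) × ICC(outcome) × ICC(CtD)
- True SE / reported SE = √DE
- Effective N = 76,505 / DE
- Actual two-sided type I error = 2 × [1 − Φ(1.96/√DE)]

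The plan does not state sidedness; two-sided is assumed. If either ICC is zero, DE = 1 and the error stays at 5%.

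**Inputs.** K and both ICCs are assumptions, since the documents give none of them.

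| K | m | ICC outcome / CtD | DE | SE ratio | Effective N | Type I error |
|---|---|---|---|---|---|---|
| 400 | 191 | 0.01 / 0.05 | 1 + 190.3 × 0.0005 = 1.095 | 1.05 | about 69,900 | 6.1% |
| 200 | 383 | 0.02 / 0.10 | 1 + 381.5 × 0.002 = 1.763 | 1.33 | about 43,400 | 14.0% |
| 150 | 510 | 0.05 / 0.20 | 1 + 509.0 × 0.01 = 6.090 | 2.47 | about 12,600 | 42.7% |

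A wider grid of assumptions (20 to 500 clusters, outcome ICC 0.01–0.05, CtD ICC 0.02–0.20) gives a type I error from 5.4% (500 clusters, 0.01/0.02) to 75.4% (20 clusters, 0.05/0.20).

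**Simulation with no true effect.**
- 600 replicates at an assumed 90% mortality. With 200 clusters and ICCs 0.02/0.10, the SE ratio was 1.32, naive rejection 15% and cluster-robust rejection 6%. With 150 clusters and 0.05/0.20, the figures were 2.43, 43% and 6%.
- A separate set of 400 replicates per setting, with cluster effects on the log-odds scale. With SD 0.4 for CtD and 0.3 for outcome, naive rejection was 17%, 8.8%, 5.8% and 4.5% for 20, 100, 200 and 500 clusters. With SD 0.8 and 0.4 it was 44%, 22%, 13% and 13.5%. Cluster-robust rejection lay between 3.5% and 7.3% throughout (Monte Carlo SE about 1 percentage point near 5%).

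**Smallest odds ratio reaching P<0.05 under independence.** Assuming 90% mortality and a share q of patients in one CtD group, SE(log OR) ≈ 1/√(76,505 × 0.9 × 0.1 × q(1 − q)).
- q = 0.5: SE 0.0241, OR exp(1.96 × 0.0241) = 1.05
- q = 0.2: SE 0.0301, OR 1.06
- q = 0.1: SE 0.0402, OR 1.08

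**The case against.** A reader might infer that CtD time and survival are known to cluster, so that every interval in the study will be wrong. The documents do not support that. They never say that either quantity varies by service, region or hospital. Section 3.1 only says who built the registry, and Section 2.6 only defines the interval. Clustering is a sound inference from how exposure and outcome arise, but its size cannot be derived.

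The plan may also be silent rather than wrong. Naming Cox and logistic regression does not rule out a robust variance, and the open covariate list leaves room for a region term. That is fair. But nothing is pre-specified, and an analyst who follows Section 3.6 as written would by default obtain ordinary standard errors.

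The upper illustration is demanding. With mean survival of 10% and normally distributed log-odds effects, an outcome ICC of 0.05 implies that the middle 95% of clusters range from about 2% to 28% survival; an ICC of 0.02 implies about 4% to 20%. The milder simulation setting showed almost no inflation at 200 or 500 clusters. This stands: the figures are scenarios, not estimates.

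Nor does 76,505 describe every analysis. It is an expected number. The matched set will normally be smaller, and a 24-hour landmark normally keeps only patients still alive then. Smaller clusters lower the design effect.

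Finally, a reader might expect a robust variance to deal with differences between areas altogether. It corrects the standard error only. Confounding by area remains, and a random intercept removes it only in part. Receiving hospital also helps to determine CtD time, so conditioning on it may change the effect being estimated. Without clustering, the robust variance approximates the ordinary one rather than equalling it.

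The missing ICC is no reason to leave the point alone, because a cluster-robust variance is estimated from the data and needs no assumed ICC.

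**Conclusion.** The point holds in conditional form. The plan states no method for clustering. If CtD time and outcome both vary between EMS services, regions or hospitals, the planned standard errors are too small and the 0.05 threshold is crossed too often. The inflation could be trivial or severe: type I error is about 6%, 14% or 43% in the three illustrations, which rest on assumed cluster counts, assumed ICCs, equal cluster sizes and the full expected sample. Nothing in the documents shows where this registry lies in that range. The change is worth making because it is cheap and kept the error close to nominal in the simulations, not because a particular amount of bias has been shown.

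**What to change.** Add to Section 3.6, in substance: *Cox and logistic models, including those fitted in the matched set, use cluster-robust (sandwich) standard errors by receiving hospital, or by EMS region if hospital is not available in the extract. A small-sample correction is applied if clusters are few, and the matched-set variance also allows for the matched pairs. The decision at P<0.05 rests on these standard errors; the log-rank test is descriptive.*

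Report a model with a region or hospital effect only as a sensitivity analysis. State beside it that the robust variance does not remove confounding by area, and that conditioning on hospital may change the effect being estimated.

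The cost is a short addition to the SAP, a little more analysis work (pairs that span hospitals need clustering in two ways) and somewhat wider confidence intervals. No new data are needed if the extract carries a hospital or region code. The documents do not show that it does, so this should be confirmed first.

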Call to Door Timing in Out-of-hospital Cardiac Arrest

Study Protocol

Version No: 1.0.0

Document Date: May 1, 2023

NCT05724914

Table of Contents

1. Background	3
2. Methods	4
3. Statistical Analysis Plan	5

1. Background

Out-of-hospital cardiac arrest (OHCA) remains a significant global health challenge, with survival rates showing modest improvement but still remaining low. The chain of survival, including early recognition, initiation of CPR, rapid defibrillation, and effective advanced life support, is crucial for improving survival rates in sudden cardiac arrest cases. Efforts to reduce emergency medical services (EMS) response times have been instrumental in enhancing survival rates during the pre-pandemic period.

Recent studies have revealed that the coronavirus disease 2019 (COVID-19) pandemic has adversely affected EMS response times, potentially leading to delayed treatment for patients with OHCA. This has coincided with a sharp increase in OHCA mortality during the COVID-19 pandemic era. However, there is a lack of data regarding the clinical implications of the time delay from first emergency call to hospital arrival on the prognosis of OHCA patients. Therefore, this study aims to investigate the impact of time from call to hospital arrival (CtD time) on clinical outcomes in patients experiencing OHCA.

2. Methods

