3.2. Analysis objectives

The primary objective of the analysis is to investigate the impact of call-to-door (CtD) time on the clinical outcomes of patients experiencing OHCA. The study aims to discern the influence of delayed hospital arrival on survival rates and neurological outcomes, considering the potential exacerbations brought about by the COVID-19 pandemic.

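### The only call-to-door grouping is <30 versus ≥30 minutes, without a rationale, and no specified analysis shows how the risk of death changes with delay

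*Combined protocol and SAP*

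**What the plan says.** The Background says that the study will "investigate the impact of time from call to hospital arrival (CtD time) on clinical outcomes in patients experiencing OHCA", and section 3.2 repeats this as the primary objective: "investigate the impact of call-to-door (CtD) time on the clinical outcomes of patients experiencing OHCA". Hypothesis 1 in section 2.6 concerns "a delayed time interval between primary emergency call and hospital arrival" and its association with survival and neurological outcome. Hypothesis 3 aims to "explore and quantify the impact of various delayed factors on the prognosis of patients experiencing OHCA". Section 3.4 fixes the endpoint: "The primary outcome is death from any cause at hospital discharge".

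Section 3.6 attaches a cut-point to CtD once, for Kaplan–Meier: "the survival curves were compared between CtD time of <30 min and CtD time of ≥ 30 min groups by the log-rank test". The descriptive tests compare two groups, presumably the same two. The models are named without the form of the exposure: "The Cox proportional hazards regression and logistic regression model were used to assess primary and secondary outcomes", and "Propensity-score matching and multivariable analyses were also utilized to adjust for confounding variables and assess the impact of CtD time on clinical outcomes". The 24-hour landmark divides follow-up after arrival, not CtD. Nowhere do the documents mention an effect per minute, further categories, a trend test or a spline, and they give no source for 30 minutes.

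**The concern.** CtD is a measured interval, and its effect on outcome is the question the study asks. One ratio across one unexplained cut answers whether later arrivals die more often. It does not say whether risk climbs before 30 minutes, after 30 minutes or throughout, or whether anything particular happens at 30. A reader who sees only that ratio may take 30 minutes for a threshold that the analysis never examined.

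The regression models might fill the gap, but the plan does not say so. If they use a single per-minute term, that term gives a slope and imposes a straight line on the logit or log-hazard scale without testing it.

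**Working it through.** **1. The plan's own figure.** Section 2.5 expects 76,505 eligible patients out of 182,508. 182,508 × 0.42 = 76,653, which is 0.2% higher. Summing the listed exclusions (28 + 0.5 + 25 + 4 = 57.5%) gives 182,508 × 0.425 = 77,566, which is 1.4% higher. The figure reproduces, and N = 76,505 is used below.

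**2. Assumptions.** The documents give no mortality, CtD distribution or effect size. Base case, assumed: 90% mortality, CtD normal with mean 30 and SD 10 minutes, two-group odds ratio (OR) 1.30, no covariate adjustment.

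**3. Different curves, same OR.** Let logit p(t) = a + b·f(t), with f(t) = t − 30 (straight line), 1 if t ≥ 30 and otherwise 0 (step), min(t − 30, 0) (rise only before 30), or max(t − 30, 0) (rise only after 30). For each shape, a and b are solved so that overall mortality is 90% and odds(≥30)/odds(<30) = 1.30. All four then give group mortalities of 88.82% and 91.18%, that is odds of 7.95 and 10.33, ratio 1.30. They differ within the groups:

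| Shape | Mortality (%) at 20 / 29 / 31 / 40 min | Change 20→29 (points) | Change 31→40 (points) | OR at a 25-min cut | OR at a 35-min cut |
|---|---|---|---|---|---|
| Line | 88.53 / 89.95 / 90.24 / 91.47 | 1.4 | 1.2 | 1.31 | 1.31 |
| Step | 88.82 / 88.82 / 91.18 / 91.18 | 0 | 0 | 1.20 | 1.22 |
| Before | 88.33 / 90.92 / 91.18 / 91.18 | 2.6 | 0 | 1.41 | 1.22 |
| After | 88.82 / 88.82 / 89.17 / 91.86 | 0 | 2.7 | 1.20 | 1.44 |

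**4. Range.** The shape calculation was repeated over 54 settings, with OR 1.30 throughout: mortality 85, 90 or 95%; median CtD 25, 30 or 35 minutes; SD 8, 10 or 12; normal or lognormal. The 20-to-29-minute change is 0.6–2.9 points for a line and 0 for a step or a rise only after 30. For a rise only before 30 it is 0.9–6.7 points (normal) or 1.1–10.1 (lognormal, where 10.1 is a single corner case).

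**5. Could a spline detect non-linearity?** Take five knots at the 5th, 27.5th, 50th, 72.5th and 95th percentiles. The noncentrality is λ = 2N × (expected log-likelihood per patient of the spline model − that of the linear model). Power = P(noncentral χ² with 3 df and λ > 7.81). At OR 1.30, λ = 24.5 (step), 62.1 (before) and 71.1 (after).

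| Two-group OR | Step | Before | After | Lowest over 54 settings × 3 non-linear shapes |
|---|---|---|---|---|
| 1.30 | 99% | >99.9% | >99.9% | 76% |
| 1.20 | 83% | 99.9% | 99.9% | 40% |
| 1.15 | 59% | 96% | 97% | not run |
| 1.10 | 29% | 69% | 72% | 13% |

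**6. Four knots or five.** At OR 1.30, four knots are slightly more powerful in about 70% of the 162 setting-by-shape combinations, including the base-case step (99.7% against 99.2%) and the five-knot worst case (80% against 76%). Five knots have the better worst case: 76% against 57%. The 57% arises for a step with lognormal CtD, median 25, SD 8 and 95% mortality, where five knots give 82%.

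**The case against.** The strongest reply is that this is under-specification and nothing more. The plan names Cox, logistic and multivariable models to assess CtD, and CtD may well enter them in minutes. This stands in part. A reader might infer that the plan dichotomises CtD everywhere or excludes a continuous analysis. The documents do not support that, because the 30-minute split is explicit only for the log-rank comparison. But even a linear term would not reveal the shape, so stating the form of CtD would not by itself close the gap.

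A second reply is that the plan never promised a delay–risk curve. A reader might take hypothesis 3 as such a promise. It speaks of delay factors in general and does not name CtD, so it gives only weak support. Hypothesis 1 is a question of association, which two groups can answer. The main support is the objective in section 3.2, and even that could be read as a delayed-versus-not contrast.

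A third reply is that the spline is no cure-all. That is right. Its non-linearity test rejects a straight line for all three alternatives without saying which one holds, a smooth curve cannot reproduce a jump, and power falls quickly as the effect shrinks. The 25- and 35-minute cuts separate the shapes only as a pair: step and rise-after both give 1.20 at 25, and step and rise-before both give 1.22 at 35.

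**Conclusion.** The point holds as an inexpensive improvement that should be made. No figure in the documents is wrong. The plan specifies one contrast at an unexplained cut, leaves the form of its main exposure open, and includes no analysis that shows where risk rises. The size of the gap is an unknown shape: under the assumptions above, one OR of 1.30 is compatible with no change, or with several points of change, in mortality across the minutes before 30.

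A reader might go further and call the two-group comparison invalid or underpowered. The calculations do not support that. For a linear effect with OR 1.10 per SD of CtD, power is 98% or more with either the cut or a linear term. Loss of power matters only for very small effects: at OR 1.05 per SD, 98% for the linear term against 55–90% for the cut, depending on the CtD distribution.

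Every magnitude here rests on mortality, CtD distribution and effect size that the documents do not give, and the power figures are before covariate adjustment.

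**What to change.** Keep the 30-minute and matched analyses. Add one pre-set analysis to section 3.6: the multivariable logistic model for death at hospital discharge, with CtD in minutes as a restricted cubic spline. Set the knots in advance. Four or five are both defensible.

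- Report the overall test (4 df with five knots, 3 with four), the non-linearity test (3 or 2 df), and the adjusted mortality curve with 95% confidence intervals at set times such as 20, 30 and 40 minutes.
- Read the shape from the curve and its intervals. A non-significant non-linearity test does not prove linearity, and a significant one does not prove a threshold at 30 minutes.
- Cuts at 25 and 35 minutes are optional sensitivity analyses, to be read together.
- State how CtD enters each Cox, logistic and multivariable model, and where 30 minutes came from.
- Recruitment ended in December 2021 and the document is dated May 2023. If outcomes have already been seen, label the spline as added later.

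The cost is SAP wording and one more model on registry data: two or three extra coefficients over a single CtD term, and one curve to report beside the ratio.

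### With no stated time zero, the Cox and log-rank results for call-to-door time depend on the clock; the primary conclusion should rest on the proportion dead at discharge

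*Combined protocol and SAP*

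**What the plan says.** Section 2.6 (Hypothesis) defines the exposure as a "delayed time interval between primary emergency call and hospital arrival", and the Background agrees. Section 3.6 compares survival curves between "CtD time of <30 min and CtD time of ≥ 30 min groups by the log-rank test". It names Cox and logistic regression together for the primary and secondary outcomes and does not assign either model to an endpoint.

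Section 3.4 reads "The primary outcome is death from any cause at hospital discharge", which is a status and not a time. It adds "death from any cause within 6 and 24 hours" with no starting point.

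No section gives a time zero, an entry rule or a censoring rule for the Kaplan-Meier, log-rank or Cox analyses. The one stated origin is in section 3.6: "Landmark analysis also was conducted at 24 hours after hospital arrival". That suggests arrival as the origin elsewhere too, but nothing says so.

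**The concern.** When the exposure is a time interval, time zero is not a neutral choice. Take two patients whose resuscitation is stopped 60 minutes after the call, one arriving at 15 minutes and the other at 50. Counted from the call, both die at 60 minutes. Counted from arrival, they die at 60 − 15 = 45 and 60 − 50 = 10 minutes, so the late arrival looks worse although the fate is the same. Conversely, if deaths are timed only after arrival and the clock starts at the call, nobody in the 30-minute-or-more group can die in the first 30 minutes. This is immortal time, and it makes delay look protective.

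A hazard ratio or log-rank P value could then reflect when death is recorded and not how many patients die. Recruitment ended in December 2021 and the document is dated May 2023, so an unstated origin also leaves a choice open after the data exist.

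**Working it through.** **Step 1. The plan's own figure.** Section 2.5 expects 76,505 eligible patients out of 182,508.
- 0.42 × 182,508 = 76,653, which is 0.2% above the stated figure.
- Subtracting the listed exclusions: 100 − (28 + 0.5 + 25 + 4) = 42.5%, and 0.425 × 182,508 = 77,566, which is 1.4% above.

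The figure reproduces. The documents give no mortality, CtD distribution or death times, so every rate below is an assumption.

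**Step 2. How small a shift reaches P < 0.05 (taken as two-sided).** Assume 90% die: 0.9 × 76,505 = 68,855 deaths. With a share q in the late group, SE(log HR) ≈ 1/√(deaths × q × (1 − q)).
- q = 0.5: SE = 0.0076, and 1.96 × SE = 0.015, so an HR of about 1.015 or 0.985 is significant.
- q = 0.3: SE = 0.0083, and 1.96 × SE = 0.016, so about 1.016 or 0.984.

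A distortion of under 2% is enough.

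**Step 3. Same patients, only the clock changed.** Entries are Cox HRs for 30 minutes or more against less.

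| Mechanism (assumed) | From arrival | From call | From call, entry at arrival |
|---|---|---|---|
| A. Equal mortality; early deaths timed from arrival | 0.99–1.01 | 0.78–0.98 | 1.07–1.39 |
| B. Equal mortality; early deaths when resuscitation stops, timed from the call | 1.42 (95% CI 1.38–1.46) | 0.96 (0.93–0.99) | 1.05 (1.02–1.08) |
| C. Hazard depends only on time since the call, among those alive at arrival | 0.94–0.98 | 0.93–0.96 | 1.00 |
| D. As A, but 88% against 91% die | 1.07–1.11 | 0.85–1.06 | 1.15–1.53 |

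- A and D: n = 76,505; CtD lognormal with median 25 or 30 minutes and log-SD 0.35 (30% or 50% late, mean gap between groups about 17 minutes); 50% or 80% of deaths early, at a mean of 20, 40 or 90 minutes after arrival; one data set per cell. A has 90% mortality in both groups.
- B: n = 20,000; median CtD 29 minutes; 90% mortality; 85% of deaths at about 60 minutes after the call, SD 12. Observed discharge mortality was 90.2% and 90.0%.
- C: n = 76,505; median CtD 27 minutes; Weibull shape 0.3, 0.5 or 0.7.
- D: the true discharge odds ratio is (0.91/0.09)/(0.88/0.12) = 1.38. The call clock reverses the direction only when 80% of deaths are early with a mean of 20 or 40 minutes.

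Sensitivity of B, arrival clock: three rebuilt runs gave 1.42–1.48; stopping at a mean of 45 or 75 minutes gave 1.43 and 1.37; 50% early deaths gave 1.10; 20% early gave 1.02 (0.99–1.05); mean 120 with SD 60 gave 1.11. With SD 30 the arrival clock gave 1.20 and the call clock with delayed entry gave 1.25.

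A further rerun with no CtD effect on fate gave 1.00–1.44 from arrival, 0.76–1.00 from the call and 1.03–1.38 with delayed entry.

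**Step 4. What does not move.** Across A and D, changing between the arrival and call clocks moved the 6-hour odds ratio by at most about 0.03 (for example 1.162 to 1.136), the 24-hour odds ratio by about 0.01, and the 24-hour landmark HR by about 0.005 (1.270 to 1.275). The logistic odds ratio for death at discharge uses no clock and did not change.

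**The case against.** The strongest defence is that the primary outcome is a status at discharge, logistic regression is named, and that result has no clock. This stands and limits the concern. It does not remove it, because section 3.6 names Cox for the same outcomes and nothing says which model carries the conclusion.

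Second, arrival is the natural reading, so immortal time threatens only a clock that the plan never mentions. This stands in part: no section says that arrival applies beyond the landmark, and arrival itself gave a false 1.42 under B.

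Third, the sizes rest on assumed death times. This also stands. The 1.42 needs most deaths tightly clustered around one time after the call; with 20% early deaths the arrival clock gave 1.02.

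Two stronger readings are tempting, and the documents support neither.
- A reader might infer that the call clock with delayed entry is the correct primary analysis. It was unbiased only under C. Under A and B it showed false harm, in the direction of the plan's own hypothesis, and with SD 30 it was worse than the arrival clock.
- A reader might infer that the landmark sentence or the 6- and 24-hour endpoints are themselves faulty. They barely move. The landmark sentence matters only as the plan's sole stated origin. Delayed entry has no meaning for a binary endpoint in logistic regression.

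**Conclusion.** The point holds for the Cox and log-rank results only. With no CtD effect on fate, the hazard ratio was about 1.00–1.45 from arrival, 0.76–1.00 from the call and 1.03–1.38 from the call with delayed entry (single runs reached 1.48 and 1.39). At the planned size, shifts of under 2% are significant. Mechanism C adds that the arrival clock can also err downwards. These figures assume many deaths in the first hour or two, timed after arrival, which the documents neither confirm nor exclude.

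A reader might go further and infer that the plan's primary result is invalid, or that the clock will reverse the true effect. Neither follows: death at discharge as a proportion does not depend on the clock, and reversal appeared only when early deaths dominated. Being independent of the clock does not make the logistic result free of confounding or of selection at arrival, which are separate questions. The plan should be changed here, but the gap does not undermine the primary outcome as worded.

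**What to change.** - Make the adjusted logistic analysis of death at hospital discharge (odds ratio or risk difference) the sole basis for the primary conclusion.
- State hospital arrival, the plan's only given origin, as time zero for Kaplan-Meier, log-rank, Cox and the 6- and 24-hour deaths, and say how deaths at or before arrival are counted.
- Report the call clock with delayed entry at arrival as a sensitivity analysis, for Cox only.
- Label Cox and log-rank results as supportive, and claim no CtD effect from them unless the proportion dead at discharge agrees.

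The cost is a few sentences in sections 3.4 and 3.6, a little more analysis and a less prominent hazard ratio. Call and arrival times are already needed to compute CtD, and the planned SAS and R software supports delayed entry. The sensitivity analysis also needs death times recorded to the minute, which the documents do not confirm; if they are coarser, it should be dropped and the limitation stated.
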